6.2.8. Unscheduled Visits

Any visits or procedures performed beyond those specified within the protocol must be documented in the Unscheduled Visit pages of the eCRF. Unscheduled visits may include, but are not limited to, reporting and/or follow-up of AEs/SAEs, changes in concomitant

medications, follow-up of subjects receiving rescue or IOP-lowering medications or ophthalmic assessments as deemed appropriate by the Investigator.

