9.4.2. Management of Increased IOP

Criteria for Starting IOP-Lowering Medication

Investigators should use the following criteria to determine whether to start IOP-lowering medication:

1. After randomization, an IOP > 30 mmHg
2. After randomization, an IOP ≥ 24 mmHg AND an increase of ≥ 10 mmHg from POD1/pre-dose baseline (both criteria must be met)

Initiation of IOP-lowering medication is at the discretion of the Investigator even if none of the above criteria are met, however, it is recommended that the Investigator uses these criteria to determine when to consider a subject for IOP-lowering medication.

Management

Investigator will use clinical judgment to determine the appropriate IOP-lowering medication to use and when to withdraw study drug and procedures, in consultation with the Study Medical Monitor.

After randomization and start of study drug, if a subject has an IOP > 30 mmHg the Investigator may commence non-prostaglandin-based IOP-lowering medication while continuing the study drug, with appropriate follow-up at the next planned visit or at an unscheduled visit. If IOP is < 30 mmHg at the next visit, the subject may continue on study drug. If at the next visit, the IOP remains > 30 mmHg while on IOP-lowering medication, then the study drug may be discontinued and alternative IOP-lowering medication may be started, after consultation with the Study Medical Monitor, who will then discuss with the Sponsor Medical Monitor.

After randomization and start of study drug, an IOP of ≥ 24 mmHg AND an increase ≥ 10 mmHg from the POD1/pre-dose baseline (both criteria must be met) is considered clinically significant and the Investigator should consider starting non-prostaglandin-based IOP-lowering medication while continuing the study drug, with appropriate follow-up at the next planned visit or at an unscheduled visit. If satisfactory reduction of IOP does not occur at the next visit, then the study drug may be discontinued after consultation with the Study Medical Monitor, who will then discuss with the Sponsor Medical Monitor.

Note:

Medications used for treating increased IOP will be recorded in the Concomitant Medications section of the eCRF.

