5.1.5.2 Visit windows

It is expected that all visits should occur according to the protocol schedule described in [Table C1](#) and [Table C2](#), the Schedule of Events; visits outside of this schedule will be addressed as protocol deviations. A new visit variable, AVISIT, will be defined based on the visit date relative to the date of surgery and a windowing strategy described by [Table F](#). AVISIT will only be used for efficacy variables.

Table F: Windowing Strategy:

Surgery	Day 1 post-surgery	2-6 days post-surgery	7-11 days post-surgery	12-18 days post-surgery	19-25 days post-surgery	26+ days post-surgery
Day 0	POD1	POD4	POD8	POD15	POD22	POD28

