5.1.9. Multiple Assessments at One Time Point

Where multiple assessments are recorded for a particular POD, e.g., ACC counts at the same visit or when two visits fall in the same POD window ([Table F](#)), the mean of the assessments will be calculated and used in any derivation of summary statistics. All observed data will be listed.

Note, for any efficacy endpoint:

If EOS falls in the same POD window ([Table F](#)) with another visit, the assessment obtained from that other visit, while the subject is still on study drug, will be used for the efficacy analyses.

If there are no other assessments in the same POD window ([Table F](#)) while the subject is still on study drug, e.g., within 2 days of the last dose of study drug as defined in 5.1.6.2, the EOS assessment will be used for efficacy analyses.

For any safety categorial endpoint, instead of taking the mean of all assessments within that POD window, the assessment obtained at the latest visit within that POD window will be used for that POD.

EOS assessments will not be modified in any case as mentioned in 5.1.6.2.

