5.6. Safety Analyses

Safety data will be analyzed for all subjects in the Safety population.

The safety endpoints are:

- Adverse event (AE)
- Serum cortisol concentrations (Part A)
- Clinical chemistry and hematology parameters (Part A) ([Appendix B](#))
- Intraocular pressure (IOP)
- Early Treatment Diabetic Retinopathy Study (ETDRS)

	Document Number: CLN.001.SAP	Version: 0
	Document Title: Clinical Study CPN-201 Statistical Analysis Plan	Page 23 of 35

- Best corrected Visual Acuity by pinhole method
- Slit-lamp biomicroscopy
 - Corneal edema
 - Ciliary flush
 - Bulbar conjunctival injection
- Dilated indirect ophthalmoscopy
 - Vitreous
 - Retina
 - Macula
 - Choroid
 - Optic nerve

See Section 7.2 of the protocol for detail about these endpoints. The analyses of these safety endpoints are described in the following sub-sections.

For all safety endpoints, the total number of subjects in the safety population and the summary statistics of all observed data will be calculated for each active dosing regimen and its matching vehicle placebo group and each visit as defined in the CRF. No imputation will be used.

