5.6.5. Intraocular Pressure

For both eyes at Screening and EOS, the analyses of IOP will follow the methods discussed in Section 5.3.2 for Both eyes at Screening and End of Study (EOS). The results will be presented in the top part of [Table 14.3.6.1](#) and [Table 14.3.6.2](#).

For study eye at POD1-POD22 (Part A) and POD1-POD15 (Part B), the analyses will follow the methods discussed in Section 5.3.2 for “observed data” under Study eye only. The results will be presented in [Table 14.3.6.1](#) and its CFB (Baseline = Screening for EOS; Baseline = POD1/pre-dose for other PODs) for the active and its matching vehicle placebo groups at each visit in [Table 14.3.6.2](#) and visually presented in [Figure 14.3.6.1](#).

The distribution of IOP over the ranges of <10, 10-15, 16-20, 21-25, 25-30, and >30(mmHg) for each treatment will be described by the frequencies in each range in [Table 14.3.6.3](#). The distribution of IOP increase over ranges of ≤ 0 , 1-5, 6-10, 11-15, >15 (mmHg) for the active and its matching vehicle placebo groups will be described by the frequency in each range at each visit in [Table 14.3.6.4](#).

	Document Number: CLN.001.SAP	Version: 0
	Document Title: Clinical Study CPN-201 Statistical Analysis Plan	Page 25 of 35

The number of subjects with an IOP ≥ 24 mmHg AND an increase ≥ 10 mmHg from pre-dose baseline, and the number of subjects with an IOP > 30 mmHg at any time following initiation of study drug will be summarized in the adverse event tables, [Table 14.3.1.1- 14.3.1.3](#).

All subjects' intraocular pressure information will be presented in [Listing 16.2.9.2](#) and visually presented in [Figure 14.3.6.2](#).

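### SAP 5.1.9 conflicts with 5.1.5.2 and 5.6 on how safety visits are windowed, and the by-visit ocular sign and acuity tables have no worst post-baseline summary behind them

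*SAP*

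**What the plan says.** SAP 5.1.9 covers several assessments falling in one window of Table F. The general rule is that "the mean of the assessments will be calculated and used in any derivation of summary statistics". For a categorical safety endpoint the rule is different: "the assessment obtained at the latest visit within that POD window will be used for that POD". The section also promises that "All observed data will be listed".

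Other sections of the SAP point elsewhere:

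- **5.1.5.2** says of the windowed visit variable that "AVISIT will only be used for efficacy variables".
- **5.6** summarises every safety endpoint from all observed data at "each visit as defined in the CRF. No imputation will be used". Table E gives unscheduled examinations their own visit number, 90, with no nominal day.
- **5.6.5** says that for study-eye IOP "the analyses will follow the methods discussed in Section 5.3.2 for" observed data. That part of 5.3.2 uses the Table F windows.

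Corneal edema, ciliary flush and conjunctival injection are tabulated by visit (SAP 5.6.7, Tables 14.3.6.6 to 14.3.6.8). So is acuity loss of 2 lines or more (5.6.6, Table 14.3.6.5). Two IOP events are counted in the adverse event tables, 14.3.1.1 to 14.3.1.3: above 30 mmHg, and at least 24 mmHg with a rise of at least 10 mmHg. The SAP Appendix leaves 5.1.9 unchanged.

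**The concern.** Safety and tolerability form a primary objective, and Protocol 1.4.2 describes this as the first administration of the product to humans. With about 21 subjects per arm, readers will look for single bad findings, and the by-visit tables are where arms are compared on ocular signs.

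A second examination in a window can follow a problem. Protocol 6.2.8 says "Unscheduled visits may include, but are not limited to, reporting and/or follow-up of AEs/SAEs", and Protocol 9.4.2 provides for management of raised IOP "with appropriate follow-up at the next planned visit or at an unscheduled visit". If the later value replaces the earlier one, or the two are averaged, the table shows the eye after the problem has eased. If the CRF visit governs instead, a finding made only at an unscheduled visit has no POD column. The programmer has to choose between these rules, and the choice changes what the tables show.

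**Working it through.** No stated sample size, power or error rate is at issue, so there is no figure of the plan to reproduce. The check has four steps.

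**1. When can two examinations share a window?** Scheduled ranges come from SAP Table E and Protocol Tables 2A and 2B; windows come from SAP Table F (days after surgery).

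| Visit | Scheduled days | Table F window |
|---|---|---|
| POD4 | 3–5 | 2–6 (POD4) |
| POD8 | 7–9 | 7–11 (POD8) |
| POD15 (Part A) | 14–16 | 12–18 (POD15) |
| EOT Part B | 15–16 | 12–18 (POD15) |
| EOT Part A | 22–23 | 19–25 (POD22) |
| EOS Part B | 20–22 (Table E) or 21–23 (Protocol) | 19–25 (POD22) |
| EOS Part A | 27–29 | 26+ (POD28) |

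Within each part, no two on-schedule visits share a window. The 5.1.9 rule acts only when an unscheduled, rescue, early-termination or off-schedule examination is added.

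**2. What does each reading show?** Assumed corneal edema grades in the POD8 window:

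| Sequence | 5.1.9 (latest) | 5.6 (CRF visit), POD8 column | Worst, any visit |
|---|---|---|---|
| Scheduled day 8 grade 3, unscheduled day 10 grade 1 | 1 | 3 | 3 |
| Scheduled day 8 grade 1, unscheduled day 10 grade 3 | 3 | 1 (the 3 is at visit 90) | 3 |
| Unscheduled day 7 grade 3, scheduled day 9 grade 1 | 1 | 1 (the 3 is at visit 90) | 3 |

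Each reading misses the grade 3 in two of the three sequences, and the third sequence loses it under both.

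**3. Acuity and IOP.** The acuity threshold is a logMAR change of at least 0.2 (SAP 5.6.6). Assumed changes of 0.24 then 0.04 give a latest value of 0.04 and a mean of (0.24 + 0.04)/2 = 0.14. Both are below 0.2; the worst value, 0.24, meets it.

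For IOP, assuming a baseline of 16 mmHg:

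- 34 then 18: mean (34 + 18)/2 = 26, not above 30; worst 34.
- 28 then 16: mean 22, rise 22 − 16 = 6; worst 28, rise 12, which meets the second threshold.
- 34 then 28: mean 31, still above 30. Averaging does not always hide a peak.

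In the first pair, replacing a scheduled 34 by 26 moves the mean of a 21-subject arm by 8/21 = 0.38 mmHg. The SAP Appendix added between-arm comparisons of IOP means and changes, so averaged values would feed those.

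**4. Is there a backstop?** For IOP, yes: both threshold events are adverse events under Protocol 8.1 and are counted in the adverse event tables whichever visit rule is used. For the slit-lamp signs and acuity loss, the SAP text specifies no worst post-baseline summary and no any-time count. The list of tables is not legible in the public copy, but the SAP text already assigns Tables 14.3.6.1 to 14.3.6.15 to other content. Size per event: 1/21 = 4.8% of an arm.

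**The case against.** The strongest reply is that 5.1.5.2 and 5.6 govern. Windowing is then irrelevant to safety, a bad scheduled finding stays in its own column, and the 5.1.9 sentence is a leftover. That answers the first sequence above. It does not answer the other two, and it leaves the safety sentence of 5.1.9 without a purpose and 5.6.5 pointing the other way.

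Second, adverse event reporting is a safety net. Protocol 7.3.1 makes clinically relevant deterioration an adverse event, and 8.3.1 records its worst severity. This stands in part. Protocol 8.1 lets an event that the investigator judges normal for cataract surgery stay in the source documents without further reporting. Protocol 1.4.1 lists corneal edema and ciliary and conjunctival hyperemia among reactions that surgery may explain. For those, listings keep the value but do not compare arms.

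Third, the direction of any error is not known. A reader might infer that extra visits are mostly rechecks after treatment, so that the tables understate harm, and more so in the arm with more rechecks. The documents do not support this. Protocol 6.2.8 gives an open list of reasons for unscheduled visits, and 9.4.2 concerns IOP only. Under 9.4.1 a subject who worsens may come in unscheduled and be rescued then; in that case the latest value may be the worst and 5.1.9 loses nothing.

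Fourth, a by-visit table describes status at a visit, and using the worst value there would be a matter of preference. That is fair, and it is why the remedy below is a separate summary.

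**Conclusion.** The SAP contradicts itself on whether safety data are windowed. Under either reading, a transient worse slit-lamp grade or a 2-line acuity loss can be absent from Tables 14.3.6.5 to 14.3.6.8. Under 5.1.9, IOP means and changes can also be diluted.

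A reader might go further and conclude that bad findings disappear from the ocular safety output. The documents do not support that. The rule acts only on extra or off-schedule examinations, 5.6 may keep a scheduled finding in place, IOP threshold events are counted in the adverse event tables, and all data are listed.

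The effect is one subject, or 4.8% of an arm of 21, for each affected finding. How often this would happen cannot be estimated from the documents, and the grades, pressures and acuity changes used above are assumptions. This is a cheap improvement to the display of a primary objective in an exploratory study, not evidence that safety has been understated.

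**What to change.** 1. Reconcile SAP 5.1.9 with 5.1.5.2, 5.6 and 5.6.5, and state that by-visit safety tables, including IOP, use the scheduled-visit value.
2. Add by arm a worst post-baseline row over all visits, unscheduled ones included, for corneal edema, ciliary flush, conjunctival injection and IOP.
3. Add by arm an any-time count of acuity loss of 2 lines or more from POD1.
4. Report the number of unscheduled examinations by arm.

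The data are already collected, so the cost is a few sentences in the SAP and a few added rows. The downside is that an arm examined more often has more chances to show a worse value; item 4 lets the reader judge this.

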5.1.10. Final Analyses

The final analysis will be performed when the last randomized subject has completed the final study visit, the data are monitored and cleaned, and the database has been locked and authorized for analysis. A data review meeting will precede database lock.

5.1.11. Deviations from SAP

Any deviations from the SAP will be documented and a justification given in the clinical study report.

5.2. Subject Disposition

Total number of subjects screened, proportion of screen failures, proportion of randomization failures will be presented in [Table 14.1.1](#).

The total number of subjects for each active dosing regimen and its matching vehicle placebo in each study population, namely, safety, ITT, and per protocol, will also be presented in [Table 14.1.1](#).

	Document Number: CLN.001.SAP	Version: 0
	Document Title: Clinical Study CPN-201 Statistical Analysis Plan	Page 18 of 35

Furthermore, the number and proportion of subjects who discontinued study drug prior to POD21 for Part A and POD14 for Part B will be summarized for each treatment according to reason of discontinuation in [Table 14.1.1](#).

All subjects' disposition status information, reasons of screen/randomization failure and discontinuation of study drug prior to POD21 will be presented in [Listing 16.2.1](#).

5.3. Primary and Secondary Efficacy Endpoint(s) Analysis

5.3.1. Definition of Primary and Secondary Efficacy Endpoint(s)

The **primary efficacy endpoints** are:

- Anterior chamber cell (ACC) count at POD15 (mean of two counts)
- Pain grade at POD15

Pain grade is defined as follows:

0	None: Absence of pain.
1	Minimal: Presence of minimal throbbing or aching pain (expected following cataract surgery)
2	Mild: Presence of mild throbbing or aching pain, easily tolerated.
3	Moderate: Presence of moderate throbbing or aching pain leading to the desire to use an analgesic.
4	Moderate: Presence of moderate throbbing or aching pain leading to the desire to use an analgesic.

The **secondary efficacy endpoints** are:

- Anterior chamber cell (ACC) count at PODs 4, 8 (and 22 for Part A), mean of two counts at each POD.
- ACC grade at PODs 4, 8, 15 (and 22 for Part A), mean of two grades at each POD

ACC grade is defined as the following:

0	1	2	3	4
0 cell	1-5 cells	6-15 cells	16-30 cells	> 30

- Pain grade at PODs 4, 8 (and 22 for Part A)
- ACF grade at PODs 4, 8, 15 (and 22 for Part A)

ACF grade is defined as follows:

ACF Grade	ACF Grade Used for Analyses	Description

	Document Number: CLN.001.SAP	Version: 0
	Document Title: Clinical Study CPN-201 Statistical Analysis Plan	Page 19 of 35

0	0	None
1+	1	Faint
2+	2	Moderate (iris and lens details clear)
3+	3	Marked (iris and lens details hazy)
4+	4	Intense (fibrin or plastic aqueous)

- Use of rescue medication and/or early withdrawal
- Proportion of subjects with ACC count = 0 (first measurement only) at PODs 4, 8, 15 (and 22 for Part A) without receiving rescue medication;
- Proportion of subjects who are pain-free at PODs 4, 8, 15 (and 22 for Part A) without receiving rescue medication;
- Proportion of subjects with ACF grade = 0 at PODs 4, 8, 15 (and 22 for Part A) without receiving rescue medication
- Visual acuity (ETDRS Best corrected Visual Acuity by pinhole method) at PODs 4, 8, 15 (and 22 for Part A) without receiving rescue medication

See Section 7.2 of the protocol for more details about the definitions of the endpoints.

5.3.2. Main analytical approach

The primary and secondary efficacy endpoints analyses will follow the General Consideration described in Section 5.1.

Efficacy analysis will be performed for the ITT population.

The primary efficacy endpoints and the secondary endpoints will be summarized in the same tables, figures, and listings.

Rescue and Early Withdrawal:

Rescue criteria: After randomization

- anterior chamber cells count >30 cells,
- an increase in anterior chamber cell count by > 15 cells from POD1/pre-dose baseline, or
- ≥ 2 grade of increase in ACF from POD1/pre-dose baseline.

For visits POD4 through EOS, the total number of subjects randomized, number of subjects who are still on study drug, and the number of subjects rescued for each reason and for subjects withdrawn early will be summarized in [Table 14.2.1](#) for each active dosing regimen and its matching vehicle placebo.

The denominator of each proportion is the number of subjects being randomized.

	Document Number: CLN.001.SAP	Version: 0
	Document Title: Clinical Study CPN-201 Statistical Analysis Plan	Page 20 of 35

Subjects' rescue and early withdrawn information together with reasons will be presented in [Listing 16.2.6.1](#).

Inflammation and Best Corrected Visual Acuity (BCVA) endpoints:

Both eyes at Screening and End of Study (EOS):

Although the tables for these data are numbered 14.2.xxx and listed with other efficacy endpoint tables, the analyses of parameters for eye exams at Screening and EOS visits, especially, those for the non-study-eye, are primarily considered as safety analyses and, therefore, they will be carried out for the safety population.

ACC count, ACC grade, pain grade, ACF grade, and ETDRS acuity (logMAR score) will be summarized descriptively for Screening and EOS visits for each active dosing regimen and its matching vehicle placebo. The summary statistics include total number of subjects in the safety population, mean, standard deviation, 95% confidence interval, median, Q1, Q3, minimum, and maximum of observed data. See [Tables 14.2.2.1.1-14.2.2.1.4](#), and [14.2.5.1](#).

The distribution of ACC, pain, and ACF grades for each treatment group will be described by the frequency within each grade for Screening and EOS visits. See the top part of [Tables 14.2.3.1 – 14.2.3.3](#).

Last non-missing observation from the other PODs will not be carried forward to impute missing values at EOS visit as discussed in Section 5.1.6.2.

Study eye only:

ACC count, ACC grade, pain grade, ACF grade, and ETDRS acuity (logMAR score) will be summarized descriptively in [Tables 14.2.2.2.1-14.2.2.2.4](#), and [14.2.5.2](#) for POD1-22 (Part A) and POD1-15 (Part B) by each active dosing regimen and its matching vehicle placebo. LOCF method will be used to impute all assessments after the subject stopped being on study drug to calculate mean, standard deviation, 95% confidence interval, median, Q1, Q3, minimum, and maximum. On study drug is defined in Section 5.1.6.2.

The observed data (without LOCF or any other imputation) when the subjects are still on study drug of above listed endpoints will also be summarized in [Tables 14.2.2.3.1 – 14.2.2.3.4](#), and [14.2.5.3](#). The treatment difference will also be reflected by the number of subjects that are still on study drug. PODs defined by [Table F](#) will be used for calculating the treatment group statistics.

	Document Number: CLN.001.SAP	Version: 0
	Document Title: Clinical Study CPN-201 Statistical Analysis Plan	Page 21 of 35

The same statistics will be calculated for CFB of the same endpoints, with POD1 pre-dose measure as the baseline, in [Tables 14.2.2.4.1-14.2.2.4.4](#), and [14.2.5.4](#). LOCF will be used to impute missing values and all assessments after subjects stopped being on study drug. Statistical comparison between each active dosing regimen and its matching vehicle placebo will be carried out for each visit during POD4 - POD22 (Part A) and POD4 – POD15 (Part B) using t-test and Mann-Whitney non-parametric tests noting that p-values will only be considered descriptive and hypothesis-generating.

These endpoints will also be visually presented in [Figures 14.2.2.1, 14.2.2.2, 14.2.5.1](#), and [14.2.5.2](#).

The distribution of ACC, pain, and ACF over different grades for each treatment will be described by the frequency and proportion of subjects within each grade for each active dosing regimen and its matching vehicle placebo for each visit during POD4 – POD22 (Part A) and POD4 – POD15 (Part B) in the lower part of [Tables 14.2.3.1 – 14.2.3.3](#) without LOCF. The denominator of the proportion is the number of subjects randomized. The treatment difference will also be reflected by the number of subjects that are still on study drug.

The proportion of subjects with ACC count = 0, pain-free, or ACF grade = 0 without receiving rescue medication will be calculated for each active dosing regimen and its matching vehicle placebo for each visit during POD1 – POD22 (Part A) and POD1 – POD15 (Part B) in [Table 14.2.4](#) and [Figure 14.2.4](#). The denominator will be the total number of subjects randomized in each treatment group. LOCF will be used to impute missing values and all assessments after subjects stopped being on study drug.

All subjects' inflammation and pain information will be presented in [Listing 16.2.6.2](#) and best correct visual acuity information will be presented in [Listing 16.2.6.3](#).

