10.3. Statistical Methods

10.3.1. General Approach

All analysis variables will be summarized descriptively by each dosing regimen, active and matching vehicle placebo groups, respectively, within each study part. Summary statistics for continuous measures will be defined as mean, standard deviation, 95% confidence interval, median, and range. Categorical measures will be summarized by the number and percent of subjects.

Inferential statistics for primary and secondary efficacy endpoints will include Student t-test (with normality assumption met) or Wilcoxon rank-sum test (with normality unmet) for continuous endpoints, and Chi-square test for categorical endpoints.

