10.3.2. Analysis of Efficacy

The primary analysis populations will be the ‘Intent-to-Treat’ Population. A subset of efficacy analyses will be examined for the Per-protocol Population as supportive analysis.

The primary efficacy analyses will include, for each dosing regimen, active and placebo separately, the summary statistics of:

- 1) ACC on POD15;
- 2) Pain grade on POD15;

- 3) Change from baseline (POD1/pre-dose) of ACC at POD15;
- 4) Change from baseline (POD1/pre-dose) of pain grade at POD15

Secondary efficacy analyses will include for each dosing regimen, active and placebo separately:

- 1) the summary statistics of:

- ACC on PODs 4, 8, 22/EOT (Part A) or PODs 4, 8 (Part B);
- Change from baseline (POD1/pre-dose) of ACC on PODs 4, 8, 22/EOT (Part A) or on PODs 4, 8 (Part B);
- ACC grade* at PODs 4, 8, 15, 22/EOT (Part A) or PODs 4, 8 and 15/EOT (Part B);
- Change from baseline (POD1/pre-dose) of ACC grade at PODs 4, 8, 15, 22/EOT (Part A) or PODs 4, 8 and 15/EOT (Part B);
- Anterior chamber flare grade at PODs 4, 8, 15, 22/EOT (Part A) or PODs 4, 8 and 15/EOT (Part B);
- Change from baseline (POD1/pre-dose) of anterior chamber flare at PODs 4, 8, 15, 22/EOT (Part A) or PODs 4, 8 and 15/EOT (Part B);
- Pain grade for each treatment at PODs 4, 8, 22/EOT (Part A) or PODs 4, 8 (Part B);
- Change from baseline (POD1/pre-dose) of pain grade at PODs 4, 8, 15, 22/EOT (Part A) or PODs 4, 8 and 15/EOT (Part B);
- Visual acuity (ETDRS Best corrected Visual Acuity measurement – pinhole method) at PODs 4, 8, 15, 22/EOT (Part A) or PODs 4, 8 and 15/EOT (Part B);
- Change from baseline (POD1/pre-dose) of visual acuity at PODs 4, 8, 15, 22/EOT (Part A) or PODs 4, 8 and 15/EOT (Part B)

* Anterior Chamber Cell Grade Definition:

Grade 0	Grade 1	Grade 2	Grade 3	Grade 4
0 cell	1-5 cells	6-15 cells	16-30 cells	> 30 cells

- 2) the proportion of subjects

- with ACC = 0 at PODs 4, 8, 15 and 22/EOT (Part A) or PODs 4, 8 and 15/EOT (Part B) without receiving rescue medication;

- who are pain-free at PODs 4, 8, 15 and 22/EOT (Part A) or PODs 4, 8 and 15/EOT (Part B) without receiving rescue medication;
- with AC flare grade = 0 at PODs 4, 8, 15 and 22/EOT (Part A) or PODs 4, 8 and 15/EOT (Part B) without receiving rescue medication.

Details of statistical analyses will be included in the SAP.

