5.1.1. General Statistical Analyses

All analyses will be done by each study part separately.

All analysis variables will be summarized descriptively by each active dosing regimen and its matching vehicle placebo group.

Continuous measures will be summarized as mean and standard deviation. In most cases, 95% confidence interval, median, and range will also be provided. Inferential statistics for continuous primary and secondary efficacy endpoints will include Student t-test and/or Mann-Whitney test.

Categorical measures will be summarized by counts. Due to the small sample size, the percentage of subjects will be provided only when it is necessary. The total number for the relevant population and the number of subjects who are still on study drug will be listed with the counts of categorical measures. “On study drug” will be defined in Section 5.1.6.2.

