5.1.2. Tables

All tables are organized by study part and by treatment, i.e., two treatments on each table: the active dosing regimen and its matching vehicle placebo. All statistical comparisons are between the active dosing regimen vs. its matching vehicle placebo in each study part separately.

	Document Number: CLN.001.SAP	Version: 0
	Document Title: Clinical Study CPN-201 Statistical Analysis Plan	Page 13 of 35

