16	“LOCF will not be used for “complete” subjects even if they have stopped study drug earlier than POD21 (Part A) and POD14 (Part B).”	Removed from SAP.	The change reflects the intended purpose of the LOCF analysis.
21	For changes from baseline of ACC count, ACC grade, pain grade, ACF grade, and ETDRS acuity (logMAR score), statistical comparison between each active dosing regimen and its matching vehicle	
 1. The comparison was carried out for the means of the efficacy endpoints as well. 2. For efficacy endpoints, the Pearson-Chi-Square test was used to compare the proportions of 	New Exploratory analyses added.

	Document Number: CPN-201.SAP Appendix Document Title: Clinical Study CPN-201 Statistical Analysis Plan Follow-Up	Version: 1 Page: 4 of 5
--	---	--

	
placebo will be carried out for each visit during POD4 - POD22 (Part A) and POD4 – POD15 (Part B) using t-test and Mann-Whitney non-parametric tests.
	
“resolved” subjects (‘Sustained’ Grade = 0) between each active group and its matching placebo group at POD4 and sustained at all later visits.
 
3. IOP means and changes from baseline were compared between active treatment groups and their matching placebo groups.
	
21	
Sensitivity Analyses:
 
“A subset of efficacy analyses will be examined for the per-protocol population as supportive analysis.”
	
These analyses will not be conducted.
	
Only 5 out of 132 (3.8%) subjects were excluded from Per Protocol population because of protocol deviations. The differences from the LOCF analyses of efficacy endpoints will be negligible.

21	
Sensitivity Analyses:
 
“Since only first ACC count will be used to define the proportion of subject with ACC count = 0,
	
These analyses will not be conducted.
	
The analyses will use the first ACC count - this is comparable to real-world clinical practice. Because only 6 (4.5%) subjects had

	Document Number: CPN-201.SAP Appendix Document Title: Clinical Study CPN-201 Statistical Analysis Plan Follow-Up	Version: 1 Page 5 of 5
--	---	---

	
analyses of using second ACC count and/or a combination of the two counts will be explored.”
		
different ACC counts at a visit, the other analyses are redundant.

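### For ACC count at POD15, the plan names no POD1-adjusted active-minus-vehicle difference with a confidence interval

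*SAP*

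**What the plan says.** - **Endpoint.** SAP 5.3.1 defines the primary ACC endpoint as the POD15 count, averaged over two readings. Protocol 10.3.2 includes that value in its primary analyses but also lists "Change from baseline (POD1/pre-dose) of ACC at POD15".
- **Tests.** Protocol 10.3.1 lets normality decide: "Student t-test (with normality assumption met) or Wilcoxon rank-sum test (with normality unmet) for continuous endpoints". SAP 5.1.1 loosens this: "Inferential statistics for continuous primary and secondary efficacy endpoints will include Student t-test and/or Mann-Whitney test". SAP 5.3.2 then applies both to change from POD1 at each visit: "using t-test and Mann-Whitney non-parametric tests noting that p-values will only be considered descriptive and hypothesis-generating".
- **Scales.** The SAP Appendix (Modifications) adds the raw scale: "The comparison was carried out for the means of the efficacy endpoints as well".
- **Intervals.** In SAP 5.3.2 the 95% confidence interval is one of the by-arm summary statistics. No interval for a between-arm difference is named.
- **Scope.** SAP 5.1.2: "All statistical comparisons are between the active dosing regimen vs. its matching vehicle placebo in each study part separately". SAP 2 and protocol 10.5 treat all p-values as descriptive or exploratory.

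**The concern.** A trial that tests no hypotheses produces estimates and intervals. Here the active-minus-vehicle effect on ACC count at POD15 can be read on two scales, each with two tests, and the visible text does not single out one difference with its interval. POD1 enters only by subtraction. Subtraction gives the baseline full weight whatever its correlation with POD15, and the raw comparison gives it none. With about 21 eyes per arm the arms can differ at POD1 by chance, and the two readings then disagree by that amount. What is at stake is how clearly and how precisely the effect is sized for the Phase 3 regimen choice. Type I error and validity are not in question.

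**Working it through.** **Inputs from the documents.** SAP 3 plans 21 per arm for about 20 completers at 5% dropout. This reproduces: 20/0.95 = 21.05, and 21 × 0.95 = 19.95. The Appendix total of 132 would be 132/6 = 22 per arm if arms were equal. Inclusion criterion 8 bounds the POD1 count to above 10 and at most 30. A uniform spread over 11 to 30 has SD √((20² − 1)/12) = 5.8, a useful reference.

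**Inputs assumed.** The documents give no SD and no POD1–POD15 correlation r. I take POD1 SD (s_b) 3 to 5.5, POD15 SD (s) 5.5 or 8, and r mainly 0 to 0.4.

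**Step 1: gap between the two planned estimates.** Under SAP 5.1.6.2 every subject with a POD1 value has an observed or imputed POD15 value, so both estimates use the same subjects. Raw difference minus change difference therefore equals the POD1 mean difference. Its SD is s_b × √(2/21) = 0.309 s_b.

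| s_b | SD of gap (cells) | P(gap beyond ±2 cells) | At least one of three pairs, 1 − (1 − p)³ |
|---|---|---|---|
| 3 | 0.93 | 3% | 9% |
| 4.5 | 1.39 | 15% | 39% |
| 5.5 | 1.70 | 24% | 56% |

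**Step 2: precision of the three estimates.** Per-subject variances:
- change: s_b² + s² − 2·r·s_b·s
- raw: s²
- ANCOVA: s²(1 − r²)(1 + 1/38), where the last factor is the cost of estimating the slope

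The 95% half-width is t × √(2·Var/21), with t = 2.021 (40 df), or 2.023 (39 df) for ANCOVA. With both SDs 5.5:

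| r | Change | Raw | ANCOVA | Variance saved v change | Variance saved v raw |
|---|---|---|---|---|---|
| 0 | 4.85 | 3.43 | 3.48 | 49% | −3% |
| 0.2 | 4.34 | 3.43 | 3.41 | 38% | 1.5% |
| 0.4 | 3.76 | 3.43 | 3.19 | 28% | 14% |

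Saving 14% of variance equals a 16% larger effective sample, since 1/(1 − 0.138) = 1.16.

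**Step 3: where the gain over the change score vanishes.** Same formulas:
- s_b 3, s 5.5, r 0.4: 26.05 for change, 26.08 for ANCOVA, so level.
- s_b 3, s 8, r 0.4: 53.8 against 55.2, ANCOVA about 2.6% worse.
- s_b 4.5, s 8, r 0.5 and 0.6: 48.25 against 49.26, and 41.05 against 42.04, ANCOVA about 2% worse.

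The change score does well there because the ANCOVA slope, r·s/s_b, is then close to 1.

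**Step 4: skewed counts.** In simulations of 20,000 runs per case with 56 to 58% zeros in the active arm, the ordinary ANCOVA interval covered 93.5 to 94.4%, similar to the raw t interval.

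**Step 5: strength contrast.** The unadjusted 95% half-width for 0.1% minus 0.05% is 2.021 × √(2/21) = 0.62 SD.

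**The case against.** The strongest reply is that a lead is already indicated. The endpoint is the POD15 value, the Appendix compares means, and protocol 10.3.1 has a rule for choosing the test. Against that raw comparison ANCOVA gains almost nothing unless r is moderate. This stands, and it limits the claim: the case against the raw comparison is one named estimate that allows for imbalance, more than precision. It does not settle the scale, because protocol 10.3.2 lists change as primary too.

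The imbalance is also visible. POD1 means are tabulated by arm, and an unadjusted difference can be worked out by hand from the planned means and SDs. The 2-cell threshold is illustrative, with no source in the documents.

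Counts have a floor at zero and are recorded only as above 30 at the top (protocol 7.2.1), so a mean-based lead must not displace the rank test. That is accepted in the fix. The planned means and t-tests need a value for counts above 30 as well, so this is not peculiar to ANCOVA.

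On timing, the Appendix speaks in the past tense and already reports that "Only 5 out of 132 (3.8%) subjects were excluded from Per Protocol population". Analysis may have begun, which reduces the value of naming a lead now and makes honest labelling necessary.

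A reader might infer that omitting 0.1% versus 0.05% contradicts the purpose in SAP 1, regimen selection. The documents do not support that. The objectives in SAP 1.2 are vehicle-controlled for each strength and frequency, each regimen has its own vehicle (SAP 1.1.2), and SAP 1 and 5.3.4 allow further exploratory analyses.

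**Conclusion.** The point holds as a gap in estimation and reporting. For ACC count at POD15 the collected POD1 value is not used as a covariate, and the visible text names no active-minus-vehicle difference with an interval. Because table shells are not shown, a reader should not conclude that such an interval is absent from the outputs.

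The two planned estimates can differ noticeably: gap SD 0.9 to 1.7 cells, above 2 cells in 3 to 24% of pairs, for POD1 SD 3 to 5.5 and 21 per arm. Adjustment removes the choice of scale, since ANCOVA gives the same treatment difference whether the outcome is the POD15 count or the change.

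A reader might infer that ANCOVA is always more precise than the planned change-score test. It is not. With both SDs 5.5 it saves 28 to 49% of variance for r from 0.4 to 0, but it is level or 2 to 3% worse when the POD15 SD well exceeds the POD1 SD and r is moderate. Against the raw comparison the range is −3% at r = 0 to +14% of variance (+16% of effective sample) at r = 0.4. All of these rest on assumed SDs and correlations. The recommendation rests on the baseline adjustment alone.

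**What to change.** In SAP 5.3.2, for each active–vehicle pair, add the POD1-adjusted (two-arm ANCOVA) active-minus-vehicle difference in ACC count at POD15 with 95% CI, on the same ITT set and LOCF values, as the lead descriptive estimate. Use whatever value the planned means assign to counts above 30. Keep the planned t-test and Mann-Whitney results, including the rank test that protocol 10.3.1 calls for when normality is unmet. Label the addition exploratory, and post hoc if made after unmasking.

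Optional and secondary: in SAP 5.1.2, allow one descriptive POD1-adjusted 0.1% minus 0.05% BID/QD difference at POD15 with 95% CI, from the two active arms within Part B. State that it contrasts products with different vehicles and that the interval will be wide (about 0.62 SD unadjusted).

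Cost: a few sentences and one short model per pair, with no new data or subjects. One degree of freedom per model is spent. If r is near 0 the interval is slightly wider than the raw one (3.48 against 3.43 cells at SD 5.5).
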